**Megestrol Acetate plus Metformin to Megestrol Acetate
in Patients
with Endometrial Atypical Hyperplasia
or Early Stage Endometrial Adenocarcinoma**

ClinicalTrials.gov ID: NCT01968317

Date: 17/June/2020

Synopsis of protocol

Enrolment criteria

Eligible patients will be women who 1) were 18-45 years old; 2) pathologically diagnosed with AEH or EEC (endometrioid, grade I, without myometrial invasion) for the first time; 3) willing to preserve their fertility; 4) have no signs of suspicious endometrial invasion or extrauterine metastasis by enhanced magnetic resonance imaging (MRI), enhanced computed tomography (CT) or transvaginal ultrasonography (TVUS); 5) have no contraindication for metformin, MA or pregnancy; 6) have no hormone or metformin treatment within six months before the trial; 7) not pregnant when participating in the trial; 8) have good compliance for the treatment.

The exclusion criteria were patients who have either of followed conditions: 1) allergy history or contraindications for MA or metformin; 2) being pregnant when initiating the study 3) alcoholism, severe infection, severe chronic diseases (dysfunction of heart, liver, lung or kidney); 4) with high risk of thrombosis; 5) recurrent AEH or EC; 6) other malignancy history.

All patients will be pathologically diagnosed by endometrial biopsy through dilation and curettage (D&C) with or without hysteroscopy (HSC). Pathologic diagnosis will be confirmed by two experienced gynecological pathologists according to the World Health Organization (WHO) pathological classification (2014). If their opinions differ, a seminar will be held in the pathological department for the final diagnosis. This study is approved by the Ethics Committees of Obstetrics and Gynecology Hospital of Fudan University. Before initiation of study procedures, written informed consent will be obtained from each patient regarding risks of conservative treatments and agreement of using their clinical data for research purpose.

Randomization and masking

AEH and EEC patients will be firstly stratified, and then both randomly assigned (1:1) to receive MA treatment (control group) or metformin plus MA treatment (experimental group) until complete regression or disease progression or unacceptable side effects, whichever occurs first. A computer-based procedure of simple randomization (SPSS for Mac, version 20.0; IBM) will be used for participant enrollment and randomization. Before an individual is successfully enrolled, her treatment assignment will remain concealed. This trial will be open label: patients and study physicians were aware of treatment assignment.

Outcomes

The primary end point is the accumulate CR rate within three months of

treatment. The accumulate CR rate within six, nine, twelve months of treatment, time to CR, adverse events, recurrence rate and pregnancy rate in two years are secondary end points.

Statistical analysis

For primary endpoint, a baseline CR rate of 25% in MA group and an expected CR rate of 50% in MA/metformin group were expected according to results in our previous pilot study, with a power of 0.9 at a two-sided significance level of 0.05, requiring an accrual 150 eligible patients (lost follow-up rate <5%). Relapse rate will be calculated among patients who achieved CR. Pregnancy rates will be evaluated among patients who planned to conceive once achieving CR. Continuous variables will be summarized by means and standard deviations, or median and interquartile range (IQR). Categorical variables will be presented as frequency with percentage. The intra-group differences of continuous variables will be investigated by Student's t-test or Mann-Whitney U test where appropriate. Chi-square test or Fisher's exact test will be used to analyze the difference between categorical variables. Adjusted Odds ratios (OR) and 95% CI will be estimated with Logistic regression model. Estimates of time to CR will be calculated using the Kaplan-Meier method. A 2-tailed p value of less than 0.05 will be considered as statistically significant. SPSS 20.0 (SPSS, Inc., Chicago, IL, USA) will be used for all the statistical analyses.

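### Treatment stops at complete regression, so if metformin speeds regression, crude adverse-event percentages compare unequal time on treatment and can hide a higher monthly risk

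*Combined protocol and SAP*

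**What the plan says.** The section on randomization and masking gives both arms the same rule for ending treatment: "until complete regression or disease progression or unacceptable side effects, whichever occurs first". Time on treatment therefore depends on how soon CR occurs.

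The primary endpoint in Outcomes is cumulative CR within three months, and Statistical analysis assumes "a baseline CR rate of 25% in MA group and an expected CR rate of 50% in MA/metformin group". Later follow-up of CR is also planned: "The accumulate CR rate within six, nine, twelve months of treatment".

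AEs appear once, in the list "time to CR, adverse events, recurrence rate and pregnancy rate in two years are secondary end points". No AE definition or denominator is given. The closing two-year limit attaches most naturally to pregnancy, or to recurrence and pregnancy; it could be read to cover AEs as well.

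No method is assigned to AEs by name. The general rules that would fit them are "Categorical variables will be presented as frequency with percentage", "Chi-square test or Fisher's exact test will be used to analyze the difference between categorical variables" and "Adjusted Odds ratios (OR) and 95% CI will be estimated with Logistic regression model". The one time-based method, Kaplan-Meier, is assigned to time to CR. The text is headed "Synopsis of protocol".

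**The concern.** If the trial succeeds as designed, more women in the metformin arm stop treatment early. An event that can occur at any time on treatment then has less opportunity to occur in that arm. Shorter treatment can offset a higher monthly event rate, the two crude percentages can come out similar, and a reader may conclude that adding metformin costs nothing in toxicity. That conclusion would hold for a whole course of treatment, but it would not have been shown for each month on the drug. At stake is the reading of one secondary endpoint.

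**Working it through.** **The plan's own figure.** With 25% vs 50%, two-sided 0.05 and power 0.9, the unpooled formula gives (1.960 + 1.282)² × (0.25×0.75 + 0.50×0.50) / 0.25² = 73.6, so 74 per arm and 148 in total. The pooled formula gives 77 per arm, 154 in total. The stated 150 is consistent with either, so 25% vs 50% at month 3 and about 75 per arm are used below.

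**From the documents:** the stopping rule, the month-3 CR rates, and the 3, 6, 9 and 12-month CR time points.

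**Assumed, because the documents do not say:** constant AE hazards h of 0.01 to 0.1 per month acting only on treatment; follow-up to month 12; no stops for other reasons; and CR after month 3 in one of two patterns. In the first, 25% vs 50% repeats in every quarter. In the second, both arms have the same later quarterly CR probability (25%, 37.5% or 50%). CR is taken either to stop treatment at 3-monthly points or as soon as it occurs (continuous).

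**Mean months on treatment, gain repeating.**
- 3-monthly: 3 × Σ(1−p)^i for i = 0 to 3. MA: 3 × (1 + 0.75 + 0.5625 + 0.4219) = 8.20. With metformin: 3 × (1 + 0.5 + 0.25 + 0.125) = 5.63. Ratio 0.69.
- Continuous: CR hazard l = −ln(1−p)/3, which is 0.0959 vs 0.2310 per month; mean = (1 − e^(−12l))/l = 7.13 vs 4.06. Ratio 0.57.

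**Crude AE proportion.**
- Continuous: h/(h+l) × (1 − e^(−12(h+l))), applied quarter by quarter when the CR rate changes.
- 3-monthly: sum over quarters of the proportion still on treatment and event-free at the start of the quarter, times (1 − e^(−3h)).

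The hidden hazard ratio (HR) is the monthly AE hazard ratio, metformin arm to MA arm, at which the two crude proportions are equal.

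| CR pattern | Months on treatment, 3-monthly | Months on treatment, continuous | Exposure ratio (3-monthly / continuous) | Hidden HR, 3-monthly | Hidden HR, continuous |
|---|---|---|---|---|---|
| Gain repeats each quarter | 8.20 vs 5.63 | 7.13 vs 4.06 | 0.69 / 0.57 | 1.47-1.51 | 1.78-2.00 |
| Equal later CR, 25% | 8.20 vs 6.47 | 7.13 vs 5.18 | 0.79 / 0.73 | 1.28-1.35 | 1.40-1.64 |
| Equal later CR, 37.5% | 7.54 vs 6.02 | 6.23 vs 4.58 | 0.80 / 0.74 | 1.26-1.31 | 1.38-1.55 |
| Equal later CR, 50% | 6.94 vs 5.63 | 5.45 vs 4.06 | 0.81 / 0.74 | 1.24-1.28 | 1.35-1.48 |
| First 3 months only | 3.00 vs 3.00 | 2.61 vs 2.16 | 1.00 / 0.83 | 1.00 | 1.21-1.23 |

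**Examples at h = 0.05, continuous stopping.** With the gain repeating, a true doubling of the monthly hazard gives crude risks of 28.3% vs 29.6%. With later CR equal at 25%, a true HR of 1.5 gives 28.3% vs 28.5%.

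**Early events.** If identical events are confined to month 1, the crude difference is 0 with 3-monthly stopping and at most about 2 percentage points with continuous stopping.

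**What a time-based analysis can detect.** In simulations with 75 per arm, HR 2 and the gain repeating (3-monthly / continuous), Cox power at h = 0.05 is 0.70 / 0.59, against 0.16 / 0.05 for chi-square on crude percentages. For less common events, log-rank power is about 0.42 / 0.34 at h = 0.02 and 0.25 / 0.21 at h = 0.01.

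**The case against.** The strongest reply is that crude percentages are not wrong. They estimate the risk of a treat-to-CR course as assigned, and a lower risk because treatment ends sooner is a real benefit. The plan states no per-month safety question. This stands, and it is why the percentages should stay.

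Second, the text is a synopsis. An AE window or safety analysis may sit in a fuller document, and the use of crude percentages for AEs is inferred from the rule for categorical variables. A reader might infer that the trial commits itself to percentages alone, or intends to conclude that metformin adds no toxicity. The text says neither.

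Third, the size rests on CR after month 3, for which the plan gives no rates. Repeating 25% vs 50% each quarter implies 12-month CR of 1 − 0.75⁴ = 68% vs 1 − 0.50⁴ = 94%, which nothing in the documents supports. A reader might take a hidden doubling as the expected size; it is the top of one scenario. With equal CR rates after month 3 the effect is clearly smaller, and within three months it is nil or slight. The direction survives for events that accrue with time on treatment.

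**Conclusion.** The point holds as a limited one. The stopping rule and the expected CR rates imply less time on treatment with metformin if it works, and no listed method that fits AEs takes this into account. The hidden monthly HR to month 12 ranges from about 1.24 to 2.0 across the scenarios above, and depends on when CR stops treatment and whether the CR gain persists. These figures are illustrations under constant hazards acting only on treatment. Early-onset events are little affected, and a small CR gain would leave little imbalance.

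The documents do not support calling the crude comparison invalid, and the stopping rule itself is not in question. This is a minor improvement to the analysis of one secondary endpoint.

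**What to change.** In the statistical section:

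- Keep the crude AE percentages, labelled as risk per treatment course, and state the AE collection window.
- Report time on treatment by arm: median and total patient-months.
- Add time to first AE over on-treatment time, with Kaplan-Meier curves and a Cox HR with 95% CI, and give the number of stops for side effects by arm.
- Exposure-adjusted rates may be shown, but not as a rate ratio alone. If equal numbers of events occurred at the very start, dividing by the repeating-gain exposures would give a spurious ratio of 8.20/5.63 = 1.46 or 7.13/4.06 = 1.76 against metformin.
- State that similar crude percentages do not by themselves show that metformin adds no toxicity.

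The cost is a few sentences and one more table. AE onset dates and treatment-stop dates must be recorded; CR dates are already needed for time to CR. Two limits should be stated. Power is low for uncommon events: where about 7% to 15% of controls are affected (h = 0.01 to 0.02), the test would usually miss a doubling. Censoring at the end of treatment may also be informative, because unacceptable side effects are themselves a reason to stop. The primary endpoint and the sample size do not change.

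### Simple randomization within AEH and EEC strata does not balance diagnosis between arms; the statistical cost is small, but the allocation method and the role of diagnosis in the analysis need correcting

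*Combined protocol and SAP*

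**What the plan says.** The *Randomization and masking* section makes two consecutive statements about allocation. The first makes diagnosis a stratification factor: "AEH and EEC patients will be firstly stratified, and then both randomly assigned (1:1"). The second gives the method: "A computer-based procedure of simple randomization (SPSS for Mac, version 20.0; IBM) will be used for participant enrollment and randomization". No blocks, block sizes, minimisation or fixed totals per stratum are mentioned. The same section says that the trial is open label and that each assignment stays concealed until the woman is enrolled.

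The *Outcomes* section makes cumulative CR within three months the primary endpoint, with both diagnoses pooled. The *Statistical analysis* section compares categorical variables by chi-square or Fisher's exact test. It also announces adjusted odds ratios from logistic regression but lists no covariates. No stratified test is named, and diagnosis has no stated role in the analysis.

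**The concern.** Stratified randomization is meant to hold the mix of a prognostic factor nearly equal between arms. It does so only if allocation within each stratum is restricted, for example by blocks. Simple randomization is unrestricted, so the two statements together describe a design without the property that the first one implies.

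The trial pools a precancer and a cancer in one comparison. By stratifying on diagnosis, the sponsor has marked it as worth balancing. If the two diagnoses regress at different rates, a chance excess of EEC in one arm moves the observed difference in CR. As the plan stands, diagnosis is controlled neither by the allocation nor by any commitment in the analysis, yet a reader would take balance to be built in.

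**Working it through.** **Inputs from the plan** (*Statistical analysis* section): "a baseline CR rate of 25% in MA group"; "an expected CR rate of 50% in MA/metformin group"; "with a power of 0.9 at a two-sided significance level of 0.05"; 150 patients in total.

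**Inputs assumed**, because the plan gives neither the diagnosis mix nor CR by diagnosis: a smaller stratum of n = 20, 30 or 50 out of 150, and a CR gap between diagnoses of 20 to 30 points.

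**1. The plan's own figure.**
- Unpooled variance: n per arm = (1.960 + 1.282)² × (0.25×0.75 + 0.50×0.50) / 0.25² = 10.51 × 0.4375 / 0.0625 = 73.6, so 74 per arm and 148 in total.
- Pooled variance: 77 per arm and 154 in total.

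The stated 150 lies between the two, before any allowance for losses. Power at 75 per arm is 0.893.

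**2. Stratified against unstratified simple randomization.** If every assignment is an independent 1:1 toss, any given sequence of 150 assignments has probability (1/2)^150, whether or not the women were first sorted by diagnosis. The two schemes are the same. Simulation agrees: the SD of the between-arm difference in EEC share was 0.066 (stratified) and 0.065 (unstratified) at 20% EEC, and 0.081 and 0.080 at 40% EEC.

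**3. Size of the chance imbalance.**
- Split within the smaller stratum, X ~ Binomial(n, 0.5).
- SD of the between-arm difference in diagnosis share, approximately 2·√(p(1−p)/150) with p = n/150. Exact enumeration agrees to within 0.001.
- Chance of a share difference of 10 points or more, by exact enumeration.

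| n | 60:40 split or worse | SD of share difference | Difference ≥ 10 points |
|---|---|---|---|
| 20 | 0.503 | 0.056 | 0.07 |
| 30 | 0.362 | 0.065 | 0.13 |
| 50 | 0.203 | 0.077 | 0.19 |

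**4. Effect on the primary difference.** The SD of the shift is the CR gap times the SD of the share difference:
- low end: 0.20 × 0.056 = 0.011
- high end: 0.30 × 0.077 = 0.023

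So it is about 1 to 2 points. The standard error of the unadjusted difference at 75 per arm is √((0.1875 + 0.25)/75) = 0.0764, or 7.6 points. It is computed from the marginal CR rates, so it already contains the chance variation in diagnosis mix. Removing that component leaves:
- low end: √(0.0764² − 0.011²) = 0.0756, a reduction of about 1%
- high end: √(0.0764² − 0.023²) = 0.0728, a reduction of about 5%

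**5. Cost of an uneven split within a stratum.** Relative to an even split, 60:40 keeps 4 × 0.6 × 0.4 = 0.96 of the information. The standard error rises by 1/√0.96 − 1, about 2%.

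**6. What restriction would achieve.** Blocks of 4 and 6 limit the imbalance within a stratum to at most 3 women, half of the larger block. In simulation with blocks of 4 and EEC shares of 10% to 50%, the difference in EEC share never exceeded 0.011 to 0.021. Under simple randomization its 95th percentile was about 0.10 to 0.16.

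**The case against.** The strongest reply is that little harm follows. Simple randomization is valid, the chi-square test keeps its level under it, and the sample size calculation already carries the noise from diagnosis mix. All of this stands. A reader might infer from the imbalance figures that the primary result would be biased, or that its error rate would be inflated. The documents do not support that: the imbalance is random and favours neither arm. A reader might also take the 50% chance of a 60:40 split in a stratum of 20 as serious, but such a split costs about 2% in standard error, and the plan specifies no comparison within a diagnosis.

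A second reply is that unrestricted allocation is the least predictable choice in an open-label trial. That is a genuine advantage, and simple randomization is defensible at 150 patients. It does not support describing the design as stratified, and randomly varying, concealed blocks keep the loss of unpredictability small.

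A third reply is that this is a synopsis, and that simple may be loose wording for separate lists with fixed 1:1 totals in each stratum. The text does not settle this, so it would go too far to assert that the allocation actually used left diagnosis unbalanced. On either reading the passage needs editing.

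A fourth reply is that adjustment in the analysis deals with chance imbalance whatever the allocation method. This is correct, but the plan does not commit to it, so it belongs in the fix.

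**Conclusion.** The point holds as a flaw in the described design, with a modest statistical consequence. That stratification followed by simple randomization adds no balance on diagnosis is an identity and rests on no assumption. It concerns allocation only. A reader might infer that the strata are useless altogether, but they could still be used in the analysis; the plan simply does not say that they will be.

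The cost is one of precision and accurate description, not validity: a possible gain of about 1 to 5% in the standard error of the primary difference. That range depends wholly on the assumed stratum size and CR gap, for which the plan offers no figures. The correction is worth making because it is cheap and because the present wording promises a balance that the stated method does not deliver.

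**What to change.** - **If enrolment is open:** replace simple randomization with permuted blocks of randomly varying size (for example 4 and 6), using separate computer-generated lists for AEH and EEC. Conceal the lists and block sizes from enrolling physicians.
- **If allocation is complete:** state the method actually used. If it was simple, do not present it as balancing diagnosis.
- **In either case:** analyse the primary endpoint with diagnosis as a factor, by a Cochran-Mantel-Haenszel test stratified by AEH/EEC or by logistic regression with diagnosis as a named covariate, in place of the unstratified chi-square or Fisher test. This also matters if blocks are adopted: when diagnosis is prognostic, an unstratified test after blocked allocation is somewhat conservative and does not use all of the precision gained.

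The cost is two new lists and a few sentences of text, with no change to the sample size. The one drawback is that blocks make some assignments slightly more predictable in an open-label trial, which varying and concealed block sizes limit.

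### The trial is open label and no masking is stated for whoever judges complete regression, so knowledge of the arm could bias the primary end point

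*Combined protocol and SAP*

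**What the plan says.** All references are to the combined protocol and SAP.

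- **Randomization and masking.** "This trial will be open label: patients and study physicians were aware of treatment assignment". The one concealment provision concerns allocation: "Before an individual is successfully enrolled, her treatment assignment will remain concealed". Assigned treatment runs "until complete regression or disease progression or unacceptable side effects, whichever occurs first".
- **Outcomes.** "The primary end point is the accumulate CR rate within three months of" treatment. CR by 6, 9 and 12 months and time to CR are secondary end points. No criterion for CR, specimen, assessor or method is given.
- **Enrolment criteria.** The entry diagnosis is made on a biopsy taken by curettage, with or without hysteroscopy, and is confirmed by two pathologists. For disagreements: "If their opinions differ, a seminar will be held in the pathological department for the final diagnosis". This text describes entry. Nothing extends it to specimens taken during treatment, and nothing says what the readers know.
- **Statistical analysis.** The sample size rests on "a baseline CR rate of 25% in MA group" and "an expected CR rate of 50% in MA/metformin group", with power 0.9 and two-sided 0.05, giving 150 patients.

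**The concern.** Allocation concealment protects against selective enrolment. It does nothing once the patient is in the trial and her response is being judged. Masked assessment is the usual safeguard at that stage in an open-label trial, and this plan states none.

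Judging regression of atypical hyperplasia or early carcinoma calls for interpretation. The provision for disagreement at entry shows that the authors expect expert readers to differ on such tissue at least sometimes. If borderline cases are called CR slightly more readily with metformin, or slightly less readily without it, the difference between arms moves in the hoped-for direction.

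The effect would reach beyond the primary end point. The later CR rates and time to CR rest on the same judgement. Relapse is calculated only among patients who reached CR, and pregnancy only among those planning to conceive after it, so misread CR also changes those denominators. Because CR ends assigned treatment, a misreading would also alter treatment duration.

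**Working it through.** **1. Is any outcome assessor masked?** Two groups are named as aware: patients and study physicians. One concealment is stated, and it ends at enrolment. Pathologists are mentioned only for the entry diagnosis, with no word on masking. So no masking of the person judging CR is stated, and no statement says that the pathologists know the arm.

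**2. Is CR a pathology reading?** This is an inference. Entry disease is defined on biopsy. Imaging appears only to rule out invasion or spread. No other means of judging regression is described. The alternative, judgement by the study physicians, leaves the end point with people stated to be unmasked. The concern holds either way.

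**3. The plan's own figure.** Inputs: 25% against 50%, two-sided 0.05, power 0.9, 1:1.
- Unpooled: n = (1.960 + 1.282)² × (0.25×0.75 + 0.50×0.50) / 0.25² = 73.6, so 74 per arm and 148 in total.
- Pooled variance under the null: 77 per arm, 154 in total.
- Power at 75 per arm: 0.893.

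The stated 150 is reproduced, before any allowance for loss to follow-up. Masking the readers does not change it.

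**4. Sensitivity to a reading shift.** Assumptions: 75 per arm (150/2), no true effect, 25% CR in the control arm, uncorrected chi-square test, and a shift in the metformin arm only. The shift sizes are assumed. Each probability sums the exact binomial probabilities of all pairs of counts that give a significant result favouring metformin.

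| CR as read, MA | CR as read, MA + metformin | Shift | Patients (shift × 75) | P(significant, favouring metformin) |
|---|---|---|---|---|
| 25% | 25% | 0 | 0 | 0.025 |
| 25% | 28% | 3 points | 2.25 | 0.060 |
| 25% | 30% | 5 points | 3.75 | 0.100 |
| 25% | 35% | 10 points | 7.5 | 0.262 |

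Hand check of the 5-point row by normal approximation:
- Pooled rate 0.275; SE under the null = √(2×0.275×0.725/75) = 0.0729.
- SE under the shift = √((0.25×0.75 + 0.30×0.70)/75) = 0.0728.
- (0.05 − 1.960×0.0729)/0.0728 = −1.28, which gives 0.10, in agreement.

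**5. The same question as a misreading rate.** Let a share f of true non-CR cases in the metformin arm be read as CR, so the shift is f × 75 points. The two-sided false-positive rate (normal approximation) is 5.0% at f = 0, 8.1% at f = 5% (3.75 points), 17.3% at f = 10% (7.5 points) and 32.0% at f = 15% (11.25 points).

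**The case against.** The strongest reply is that this is a gap in reporting and that no flaw in conduct has been shown. The sentence on awareness lists two groups and is compatible with masked pathologists. The document is headed a synopsis, where specimen handling is easily left out. That much stands, and it rules out several stronger readings that a reader might infer:

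- **That the pathologists are unmasked.** The documents are silent on them. The supported statement is that masking is not stated.
- **That CR is defined as a pathology reading.** CR is not defined at all. Histology is the likeliest basis, but it is inferred.
- **That two pathologists and a seminar read the follow-up specimens.** That procedure is written for the entry diagnosis, when no arm has been assigned. It cannot be cited as the outcome procedure, and a fix cannot assume that double reading is already in place.
- **That paperwork reaching the readers shows the arm.** No such paperwork is described.
- **That no later analysis could ever repair the bias.** If CR is histological, a masked re-reading of retained slides could replace the recorded calls. The documents do not say whether slides are kept, so this can be neither relied on nor excluded.

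It is also fair to say that the calculation shows sensitivity and is not evidence of bias in this trial. The shift is assumed, runs in one direction and affects one arm. A 10-point shift means misreading about 13% (10/75) of true non-CR cases in the metformin arm and none in the control arm, which is a strong assumption.

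What the reply does not answer is that a plan followed as written instructs nobody to keep the arm from whoever judges the primary end point. Two readers, even if used throughout, reduce random error. They do not remove a bias that both share.

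**Conclusion.** The concern holds as a potential bias. An end point that depends on judgement, in an open-label trial with no stated masking of its assessor, is exposed to assessment bias. Open-label treatment does not require unmasked reading, so the exposure can be avoided and the point goes beyond a request for detail.

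Its size in this trial is unknown. Under the assumptions listed, a shift of two to four patients in 75 would raise the chance of a false result favouring metformin from 2.5% to between 6% and 10%, and a shift of seven or eight patients to about 26%. The conclusion rests on CR being histological or else judged by the unmasked study physicians, and on silence meaning that no masking is required. It would fall away if a fuller operating document already masks the readers. The documents do not support saying that bias occurred or that the readers know the arm.

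**What to change.** Add to Outcomes, with a matching sentence under Randomization and masking:

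1. For the trial's end points, CR is determined by the histology report on follow-up specimens, with the criterion for CR stated.
2. Whichever pathologists already read those specimens, and any seminar that settles a disagreement, do so masked to treatment arm.
3. Specimens and any accompanying paperwork carry the study number and visit but not the arm. MA use can be disclosed, because both arms receive it.

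If masked reading is already the practice, the change is only to write it down.

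**Cost.** A few protocol sentences and the administration needed to keep the arm from the readers. No second reading beyond existing practice, no extra biopsy and no change to the 150 patients. Treatment stays open label.

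### Disease progression ends trial treatment but is not separately identified in any end point, and its handling in the time-to-CR analysis is not stated

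*Combined protocol and SAP*

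**What the plan says.** Under Randomization and masking, treatment continues "until complete regression or disease progression or unacceptable side effects, whichever occurs first". Progression is mentioned nowhere else in the text supplied, and it is not defined there.

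Under Outcomes, the text reads "The primary end point is the accumulate CR rate within three months of" and continues "treatment. The accumulate CR rate within six, nine, twelve months of treatment, time to CR, adverse events, recurrence rate and pregnancy rate in two years"; the items after the full stop are the secondary end points.

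Under Statistical analysis:

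- "Relapse rate will be calculated among patients who achieved CR".
- "Estimates of time to CR will be calculated using the Kaplan-Meier method". No censoring rule and no competing event are given.
- "Chi-square test or Fisher's exact test will be used to analyze the difference between categorical variables". The sentence names tests, not the variables they apply to.

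Under Enrolment criteria, "written informed consent will be obtained from each patient regarding risks of conservative treatments". Those risks are neither named nor ranked.

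**The concern.** Three events end treatment. Two of them have a matching end point: complete regression has the CR outcomes, and unacceptable side effects have adverse events. Progression has none.

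The women enrolled have AEH or grade I EEC and accept conservative treatment to keep their fertility, so whether disease worsens on treatment bears directly on that choice. A report that follows this plan could show faster CR with metformin and leave open whether progression before CR was less, equally or more frequent in that arm. The trial is open label, which is a further reason to state in advance what counts as progression and how it is reported.

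The second issue is the time-to-CR curve. A woman taken off treatment for progression is not an ordinary censored observation, because censoring assumes she has the same later chance of CR on trial treatment as those still at risk. If the analyst censors her at treatment stop, one minus the Kaplan-Meier estimate exceeds the proportion who actually reach CR. The plan neither requires nor excludes this.

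**Working it through.** **The plan's own figure.** Inputs from Statistical analysis: 25% against 50%, power 0.9, two-sided 0.05, 150 patients. With unpooled variance, n per arm = (1.960 + 1.282)² × (0.25×0.75 + 0.50×0.50) / 0.25² = 73.6, so 74 per arm and 148 in total. With pooled variance it is 77 per arm and 154 in total. The stated 150 lies between these, before any allowance for loss, and 75 per arm gives power 0.893. This point does not depend on the sample size; 75 per arm is used below only as a denominator.

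**Where a woman who progresses before CR appears.**

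- CR within 3, 6, 9 and 12 months: non-CR if she stays in the denominator, and not distinguished from persistent disease.
- Recurrence: outside the denominator, which is restricted to women with CR.
- Adverse events: nothing says progression is recorded as one.
- Time to CR: either censored at treatment stop or kept at risk without an event. The plan does not say which, and neither shows progression.

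**Precision of a progression result.** At an assumed 2% to 8%, expected events are 75 × 0.02 = 1.5 to 75 × 0.08 = 6 per arm. With no events, the exact two-sided 95% upper limit is 1 − 0.025^(1/75) = 4.8%. With 2/75 the exact interval is 0.3% to 9.3%, and with 4/75 it is 1.5% to 13.1%. Power to separate 5% from 10% at 75 per arm is about 0.21, so the result would be descriptive.

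**Size of the effect on the curve, if progressors are censored at treatment stop.** Assumptions: constant hazards, and the plan's three-month CR rates used to set the CR hazard.

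- CR hazard λ = −ln(1 − CR at 3 months)/3. This is −ln(0.75)/3 = 0.0959 per month at 25%, and −ln(0.50)/3 = 0.2310 at 50%.
- Kaplan-Meier target at month t: 1 − exp(−λt). At month 12 this is 68.4% and 93.8%.
- Cumulative incidence of CR: λ/(λ+h) × [1 − exp(−(λ+h)t)]. The progression hazard h is solved so that h/(λ+h) × [1 − exp(−12(λ+h))] equals the assumed progression by month 12.
- Example, 25% rate with 5% progression: h = 0.00726, λ+h = 0.10315, and (0.09589/0.10315) × (1 − exp(−1.2378)) = 66.0%.

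| 3-month CR | Progression by month 12 (assumed) | Kaplan-Meier, month 12 | Cumulative incidence, month 12 | Excess (points) |
|---|---|---|---|---|
| 25% | 2% | 68.4% | 67.4% | 0.9 |
| 25% | 5% | 68.4% | 66.0% | 2.4 |
| 25% | 8% | 68.4% | 64.6% | 3.8 |
| 50% | 2% | 93.8% | 92.1% | 1.6 |
| 50% | 5% | 93.8% | 89.6% | 4.1 |
| 50% | 8% | 93.8% | 87.2% | 6.6 |

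Excesses are computed before rounding. They do not cancel between arms. The Kaplan-Meier gap at month 12 is 93.8 − 68.4 = 25.4 points. With equal progression in both arms, the cumulative-incidence gap is 92.1 − 67.4 = 24.7 at 2% and 87.2 − 64.6 = 22.6 at 8%. The curves would therefore overstate the difference between arms by about 0.7 to 2.8 points.

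At month 3, even if CR were read from the censored curve, the excess would be only 0.1 to 0.4 points at the 25% rate and 0.3 to 1.4 at the 50% rate. As a simple proportion with progressors kept in the denominator, it carries none.

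**The case against.** The strongest objection is that the plan does not say progressors are censored. It names Kaplan-Meier and stops there; it does not say that follow-up for CR ends with treatment. Keeping these women at risk to month 12 as not in CR is compatible with the text, and the curve is then not inflated. A reader might infer that progressors certainly drop out of the curve, but the documents support only that their handling is unspecified. This stands, and it makes the percentage-point figures conditional.

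A reader might also infer that progressors are counted in no end point. That goes too far: if kept in the denominator they are failures in every CR rate, including the primary. What is missing is their separate identification. Nor do the documents call progression the main oncological risk. They rank no risks, and recurrence after CR, also an oncological outcome, is listed.

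It can be said too that progression might be collected as an adverse event, or tested under the general chi-square/Fisher sentence. Either is possible, but neither is stated, so neither commits the sponsor to a result.

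Finally, the text is headed a synopsis, events would be few, and a comparison would have little power. These points limit the weight of the concern. They do not remove it, because an estimate with its interval is informative even at zero events.

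**Conclusion.** The point holds as a gap in reporting and in analysis specification. Progression before CR is a treatment-ending event that no listed end point identifies, and the time-to-CR method leaves its handling open. This follows from the text alone and needs no assumed rate.

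The size of any distortion in the curve does rest on assumptions: censoring at treatment stop, constant hazards, and 2% to 8% progression by month 12. On those terms, 12-month CR is overstated by about 0.9 to 3.8 points at the 25% rate and 1.6 to 6.6 at the 50% rate. It is confined to the Kaplan-Meier estimate. The separately listed 6-, 9- and 12-month rates, if analysed as proportions with all randomised women in the denominator, do not carry it.

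A reader might conclude that the primary comparison is compromised. The documents do not support that: the three-month proportion is essentially unaffected and the sample size is untouched. The change should be made, but it is not a condition for a valid primary test. The judgement covers only the synopsis supplied.

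**What to change.** Add one secondary end point, for example:

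> Disease progression before CR, by the sponsor's own pre-stated definition as used for the stopping rule, in all randomised patients, by arm and by AEH/EEC stratum, with exact 95% confidence intervals (descriptive).

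The definition is for the sponsor to supply; the plan needs only to state it and to use the same one for stopping and for reporting.

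Add one sentence on time to CR: progression is a competing event and cumulative incidence is reported, or women who progress stay at risk to month 12 as not in CR. Either should replace any censoring at treatment stop. With complete follow-up to month 12 the two give the same curve.

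The cost is wording and one table. The total stays at 150. Progression must already be recognised for the stopping rule to operate, but the synopsis gives no on-treatment assessment schedule, so whether extra data collection is needed cannot be judged from it. The downsides are small: few events, wide intervals, and slightly lower 12-month CR estimates than a censored curve would show.
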